## CONSENT PROCEDURES

Explain in detail how, when, where, and by whom consent is obtained, and the timing of consent (i.e., how long subjects will be given to consider participation). For most studies involving more than minimal risk and all studies involving investigational drugs/devices, a licensed physician investigator must obtain informed consent. When subjects are to be enrolled from among the investigators' own patients, describe how the potential for coercion will be avoided.

Written, informed consent will be obtained from all participants following a screening interview to determine eligibility. All subjects will be required to give informed consent and must understand all procedures prior to their participation in the study. Consent will be obtained by the principal investigator, [name], or the licensed physician investigator on the protocol, [REDACTED]. If consent is obtained by [name], a licensed physician investigator will review and sign off on patient enrollment. A physician will also be available if the patient has any additional questions during the consent process. The consent form will include a description of the study, information about procedures, and assurances of confidentiality. A member of the research staff will explain the consenting procedure and be available for any questions that arise from the consent form. Prior to signing the informed consent, subjects will be asked if they have any questions regarding the conduct or design of the study. A copy of the signed consent form will be given to the study subject, and a copy placed in their research record. All subjects will be reminded that their participation is completely voluntary, and may withdraw or discontinue the neuropsychological evaluation at any time. The informed consent will be approved by the McLean Hospital Institutional Review Board, which monitors study progress, safety and outcome on a regular basis. All signed consent forms will be kept in the subject's case report form in room 204 of the Neuroimaging Center under lock and key.

### Remote Consenting Process

We will remotely consent patients by one of the two following options. The first option will consist of consenting via REDCap using the MGB consent template. The second option is to send the participant the consent form ahead of time for their review, consent them over the phone, and have the participant physically sign or e-sign the consent form and either scan or take a photo of all pages, and send to us; this will be signed by the investigator, and a copy will be provided to the participant. In-person written consent may also occur in rare circumstances. Each subject's file will contain a note to file describing the procedure followed.

NOTE: When subjects are unable to give consent due to age (minors) or impaired decision-making capacity, complete the forms for Research Involving Children as Subjects of Research and/or Research Involving Individuals with Impaired Decision-making Capacity, available on the New Submissions page on the PHRC website:

<https://partnershealthcare.sharepoint.com/sites/phrmApply/aieipa/irb>

For guidance, refer to the following Partners policy:

Informed Consent of Research Subjects:

[https://partnershealthcare-public.sharepoint.com/ClinicalResearch/Informed\\_Consent\\_of\\_Research\\_Subjects.pdf](https://partnershealthcare-public.sharepoint.com/ClinicalResearch/Informed_Consent_of_Research_Subjects.pdf)

## DATA AND SAFETY MONITORING

Describe the plan for monitoring the data to ensure the safety of subjects. The plan should include a brief description of (1) the safety and/or efficacy data that will be reviewed; (2) the planned frequency of review; and (3) who will be responsible for this review and for determining whether the research should be altered or stopped. Include a brief description of any stopping rules for the study, when appropriate. Depending upon the risk, size and complexity of the study, the investigator, an expert group, an independent Data and Safety Monitoring Board (DSMB) or others might be assigned primary responsibility for this monitoring activity.

NOTE: Regardless of data and safety monitoring plans by the sponsor or others, the principal investigator is ultimately responsible for protecting the rights, safety, and welfare of subjects under his/her care.

Data analyses will be conducted on the open-label phase of the study prior to initiating the double-blind phase in order to ensure that patients derive clinical benefit from the dose selected. Specifically, in conjunction with [REDACTED], we will assess clinical response after the first 5 patients have completed their 6 week trial. If we do not see clinical improvement based on a review of clinical scales, subjective reports and performance, we will consider increasing the dose to 1 droppers two times a day for a total of 60 mg CBD per day. Clinical improvement will be defined as a 15% reduction in BAI scores from baseline. Findings will be used to inform the double blind phase of the study, which would not begin until adequate dose/response is achieved. An amendment would be submitted to the IRB for approval prior to adjusting the dose of CBD.

In the unlikely event that an adverse event occurs, it will be reported to the primary investigator and the Institutional Review Board's guidelines will be followed to ensure adequate reporting and response. All adverse events will be reported to the Partners Healthcare Internal Review Board for their records. There are currently no plans to utilize a Data Safety Monitoring Board (DSMB) due to the extremely low side-effect profile of CBD, but if the IRB deems that an independent DSMB is necessary, the investigators would be happy to suggest individuals who are appropriate or to consider outside suggestions from IRB members.

Subjects are required to have a structural MRI scan of clinical quality at least once per year at McLean Hospital that is reviewed by a board-certified radiologist or neurologist and a clinical report is generated usually within 2-4 days. If the subject has not received a structural clinical scan in the past year, one will be obtained for the present study. Subjects will not receive more than one structural clinical MRI within a given 12-month period unless a follow-up scan is recommended by the radiologist who reads the scan. Abnormal reports are reviewed by the Clinical Director of the McLean Imaging Center (MIC), [REDACTED] and forwarded to the Principal Investigator, in this case, [name], and the designated study physician. If an abnormality is present, the study physician and PI will coordinate the process of contacting the subject so that an appointment can be made to discuss the findings. The MIC Clinical Director may also assist with this process when requested and appropriate. If a follow-up scan is recommended by the radiologist, we will offer the subject a cost-free repeat scan (with contrast if indicated). In all cases we offer a copy both of the clinical report and the MRI scan (on film or cd) to subjects to take to their primary care or other consulting physicians, at no cost.

FMRI, DTI/DKI, and MRS data collected will be processed with software available in the Neuroimaging Center. Echo planar images will be analyzed off line using a semi-automated fMRI data analysis tool and a motion correction algorithm developed on-site at McLean. Measures of

signal intensity will be derived by averaging the signal measured in all pixels in each region of interest (ROI) for each time point during the task activation period.

Describe the plan to be followed by the Principal Investigator/study staff for review of adverse events experienced by subjects under his/her care, and when applicable, for review of sponsor safety reports and DSMB reports. Describe the plan for reporting adverse events to the sponsor and the Partners' IRB and, when applicable, for submitting sponsor safety reports and DSMB reports to the Partners' IRBs. When the investigator is also the sponsor of the IND/IDE, include the plan for reporting of adverse events to the FDA and, when applicable, to investigators at other sites.

NOTE: In addition to the adverse event reporting requirements of the sponsor, the principal investigator must follow the Partners Human Research Committee guidelines for Adverse Event Reporting

In the unlikely event that an adverse event occurs, it will be reported by the primary investigator to the Institutional Review Board, and the IRB's guidelines will be followed to ensure adequate reporting and response. All adverse events will be reported to the Partners Healthcare Internal Review Board for their records.

## MONITORING AND QUALITY ASSURANCE

Describe the plan to be followed by the principal investigator/study staff to monitor and assure the validity and integrity of the data and adherence to the IRB-approved protocol. Specify who will be responsible for monitoring, and the planned frequency of monitoring. For example, specify who will review the accuracy and completeness of case report form entries, source documents, and informed consent.

NOTE: Regardless of monitoring plans by the sponsor or others, the principal investigator is ultimately responsible for ensuring that the study is conducted at his/her investigative site in accordance with the IRB-approved protocol, and applicable regulations and requirements of the IRB.

Regulatory binders are kept for all studies at McLean Hospital in order to constantly monitor investigations and ensure that all data is collected safely.

The principal investigator will be responsible for monitoring and ensuring the integrity of the data and adherence to the IRB-approved protocol. They will review any questions or concerns regarding data, and will review each signed consent form for the study.

For guidance, refer to the following Partners policies:

Data and Safety Monitoring Plans and Quality Assurance

[https://partnershealthcare-public.sharepoint.com/ClinicalResearch/DSMP\\_in\\_Human\\_Subjects\\_Research.pdf](https://partnershealthcare-public.sharepoint.com/ClinicalResearch/DSMP_in_Human_Subjects_Research.pdf)

Reporting Unanticipated Problems (including Adverse Events)

[https://partnershealthcare-public.sharepoint.com/ClinicalResearch/Reporting\\_Unanticipated\\_Problems\\_including\\_Adverse\\_Events.pdf](https://partnershealthcare-public.sharepoint.com/ClinicalResearch/Reporting_Unanticipated_Problems_including_Adverse_Events.pdf)

## PRIVACY AND CONFIDENTIALITY

Describe methods used to protect the privacy of subjects and maintain confidentiality of data collected. This typically includes such practices as substituting codes for names and/or medical record numbers; removing face sheets or other identifiers from completed surveys/questionnaires; proper disposal of printed computer data; limited access to study data; use of password-protected computer databases; training for research staff on the importance of confidentiality of data, and storing research records in a secure location.

NOTE: Additional measures, such as obtaining a Certificate of Confidentiality, should be considered and are strongly encouraged when the research involves the collection of sensitive data, such as sexual, criminal or illegal behaviors.

Confidentiality of information collected will be maintained with the assignment of an identification number or code, which will be used in place of subject names in all data analyses and reports. Computer systems are located in the Cognitive and Clinical Neuroimaging Core. Keys showing the assignment of identification numbers to subject names will be stored with subject files in [REDACTED] under lock and key. All of the data that is collected will be kept for a minimum of seven years once the study has been completed. Only the Principal Investigator, [name], her research staff, and the study collaborators will have access to the data that is collected.

All subjects will be required to give informed consent and must understand all procedures prior to their participation in the study. Subjects are informed of their confidentiality and privacy rights in the informed consent form. To ensure that subjects' rights and safety are protected during the conduct of this research study, subjects consent to the inspection of their medical records by specifically authorized monitors. Such monitoring may be performed by the Human Research Protection Program of McLean Hospital, or by the FDA or other involved federal agency.

Subjects are informed that all the information obtained in this study will be used for research investigational purposes only. Name of subjects will never be publicly disclosed at any time. Subjects will not be identifiable in any publication that may arise from this research.

Subjects will receive a copy of the consent document to keep as well as a copy of the "Partners Healthcare Notice for Use and Sharing of Protected Health Information." Subjects will be informed that this research will be conducted and administered in compliance with all state and federal laws.

## SENDING SPECIMENS/DATA TO RESEARCH COLLABORATORS OUTSIDE PARTNERS

Specimens or data collected by Partners investigators will be sent to research collaborators outside Partners, indicate to whom specimens/data will be sent, what information will be sent, and whether the specimens/data will contain identifiers that could be used by the outside collaborators to link the specimens/data to individual subjects.

In some cases, urine samples may be sent to Quest Diagnostics to assess recent substance use. The samples will be labeled with the subject's initials, date of birth, and study ID.

Data collected during the study may be sent to [REDACTED] in order to provide public health context to our research findings. A Data Sharing Plan is on file detailing the method of sharing, security provisions, etc.

Specifically address whether specimens/data will be stored at collaborating sites outside Partners for future use not described in the protocol. Include whether subjects can withdraw their specimens/data, and how they would do so. When appropriate, submit documentation of IRB approval from the recipient institution.

Specimens will not be stored off-site for future use not described in the protocol.

#### **RECEIVING SPECIMENS/DATA FROM RESEARCH COLLABORATORS OUTSIDE PARTNERS**

When specimens or data collected by research collaborators outside Partners will be sent to Partners investigators, indicate from where the specimens/data will be obtained and whether the specimens/data will contain identifiers that could be used by Partners investigators to link the specimens/data to individual subjects. When appropriate, submit documentation of IRB approval and a copy of the IRB-approved consent form from the institution where the specimens/data were collected.

N/A

#### **STATISTICAL APPROACHES**

All statistical analyses will be conducted using IBM SPSS Statistics (version 28). Data will be screened for outliers and any data points more than 2 standard deviations from the group means will be excluded. Additionally, data will be screened for skew, kurtosis, non-normality, and homogeneity of variance. If the assumptions of parametric inferential analyses are not met, the appropriate non-parametric analyses (e.g. Wilcoxon-Signed Rank Test) will be performed. Descriptive statistics will be used to characterize the demographic data. Baseline clinical and neuropsychological data will be assessed using 2-tailed paired *t*-tests to compare follow-up timepoints to baseline values. When needed, Bonferroni corrections for multiple comparisons will be utilized.

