In order to assess the efficacy of the dose chosen for the double-blind study, we will also conduct a small open-label trial of the CBD solution prior to initiating the double-blind study. This open-label trial will enroll up to 12 participants who are interested in using CBD, and who have anxiety. This trial will determine whether patients derive clinical benefits at the current dosage proposed for the active treatment arm of the double-blind trial. This trial will examine all components of the originally proposed study.

Subjects will be recruited through IRB-approved advertisements and flyers in regions that have approved medical marijuana. Additionally, medical marijuana healthcare facilities throughout New England, including CannaCare, Integr8, MMJ Physician Practice, and others, may also refer interested patients to contact the study recruitment line for further screening. These healthcare groups provide their interested patients who meet for general inclusion criteria with study recruitment materials. The total sample size for the double-blind study is 40 (20 CBD, and 20 placebo); up to 15 of each group (30 total) will also complete the MRI scanning protocol. For the open-label trial, the total sample size is 12.

Inclusion Criteria:

- 1) Subject has provided informed consent
- 2) Subject is 18 or older
- 3) Subject is a native English speaker or acquired English prior to age 5
- 4) Subject scores a minimum of 16 on the Beck Anxiety Inventory (BAI) OR a minimum of 8 on the Overall Anxiety Severity and Impairment Scale (OASIS) at the screening visit

Exclusion Criteria:

Subjects will be excluded if they report any of the following:

- 1) Non-native English speakers
- 2) Estimated IQ < 75
- 3) Meets criteria for DSM-IV classification of current substance abuse/dependence, psychotic disorder, bipolar disorder, or an eating disorder
- 4) A first-degree relative with a psychotic disorder
- 5) A history of head injury or loss of consciousness greater than 5 minutes
- 6) Currently uses marijuana or cannabinoid-based products more frequently than 1x/month
- 7) Female subjects will be excluded if they have a positive urine pregnancy test, or if they are currently breastfeeding
- 8) Presence of a serious medical illness, including liver, kidney, or cardiovascular disease, or neurological disorder
- 9) Allergy to coconut oil

- 10) Current use of valproate
- 11) Currently enrolled in other research studies or clinical trials involving interventions

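### The compulsory 2 SD exclusion deletes valid data and, depending on how its undefined limits are set, either inflates the paired t-test's type I error or shrinks a true change (both mildly on one reading)

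*Combined protocol and SAP*

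**What the plan says.** The section Statistical Approaches says that data will be screened for outliers and that "any data points more than 2 standard deviations from the group means will be excluded". It adds three further provisions.

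- **Test.** Clinical and neuropsychological data "will be assessed using 2-tailed paired" t-tests "to compare follow-up timepoints to baseline values". No between-arm test is written.
- **Fallback.** "If the assumptions of parametric inferential analyses are not met, the appropriate non-parametric analyses" will be used, with the Wilcoxon signed-rank test as the example.
- **Multiplicity.** "When needed, Bonferroni corrections for multiple comparisons will be utilized". No family of tests is defined.

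Research Design and Methods gives the sizes: "The total sample size for the double-blind study is 40 (20 CBD, and 20 placebo") and "For the open-label trial, the total sample size is 12". The documents give no significance level, no baseline to follow-up correlation and no effect size in SD units. Nothing elsewhere defines or softens the exclusion rule.

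**The concern.** Screening that flags unusual values for checking is ordinary practice. This rule goes further, because deletion is automatic and a value need only be far from the mean.

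Three things are left open: whether the rule acts on observed scores or on changes, whether the group is a visit, an arm or a pool of these, and whether it is applied once or repeatedly. The phrase about data points reads most naturally as observed scores. Under a paired test, deleting either score of a participant removes the pair.

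The consequence depends on those choices:

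- **Limits centred on each visit's own sample mean.** Deletion makes the mean change vary more from sample to sample, while the standard error computed from the trimmed data is too small. The test rejects too often.
- **Limits pooled over both visits.** The centre lies between the two visit means. The values cut are then mainly high scores at the worse visit and low scores at the better one. These belong to pairs with large changes, so a true change is pulled toward zero.

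The same data could therefore give different p-values and estimates through a choice that the plan does not record, in groups of only 12 or 20.

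**Working it through.** The plan has no figure of its own to reproduce here.

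**Inputs from the documents:** the 2 SD limit, the two-tailed paired t-test, n = 12 (open-label) and n = 20 per arm (double-blind).

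**Assumptions:** 5% level; normal scores with SD 1; correlation r = 0.3–0.7, with 0.9 as a favourable case; one pass; true changes of 0.5, 1.0 and 2.0 SD of the score.

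**Step 1: valid values lost.** For normal data, a value lies more than 2 sample SDs from its own sample mean with probability P(|T| > t), where T has n − 2 degrees of freedom and t² = 4n(n − 2) / [(n − 1)² − 4n].

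- n = 12: t² = 480/73 = 6.58, t = 2.56, P = 0.0282. Expected loss 12 × 0.0282 = 0.34.
- n = 20: t² = 1440/281 = 5.12, t = 2.26, P = 0.0362. Expected loss 20 × 0.0362 = 0.72.

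At least one valid value is lost in about 33% of samples of 12 and 63% of samples of 20, for each variable.

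**Step 2: type I error of the paired t-test.** This was simulated with no true change, deleting values outside sample mean ± 2 sample SD and dropping a pair if either score was deleted.

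| Reading (one pass, r = 0.3–0.7) | n = 12 | n = 20 | Pairs lost (n = 12; n = 20) |
|---|---|---|---|
| No deletion | about 5% | about 5% | 0; 0 |
| Observed scores, limits per visit within group | 6.0–7.5% | 6.3–8.2% | 0.6–0.7; 1.2–1.4 |
| Observed scores, limits pooled over both visits | 5.0–5.1% | 5.0–5.1% | 0.8–0.9; 1.4–1.6 |

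At r = 0.9 the per-visit figure is 5.3–5.7% across both sizes.

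**Step 3: bias and power with limits pooled over both visits.**

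- True change 0.5 SD: estimated as 0.43–0.46, or 7–15% too small.
- True change 1.0 SD: estimated as 0.89–0.95, or 5–11% too small.
- True change 2.0 SD: about 2–5% too small.
- At r = 0.9, for 0.5–1.0 SD: 2–3% too small.
- Power at 0.5 SD, n = 20: 36–71%, against 44–78% with all data.

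Per-visit limits within a group give no such bias.

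**Step 4: other readings.**

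- Change scores within a group: about 9.5–10% type I error.
- Observed scores with limits pooled over arms, but the test run within one arm of 20: 5.7–6.6%, and a true 0.5 SD change is estimated as 0.46–0.48. Inflation and shrinkage occur together, both mildly.

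**Step 5: do the other provisions cure it?**

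- Exact Wilcoxon after per-visit deletion of observed scores: 5.3–6.4% (n = 12) and 6.0–7.6% (n = 20), against 4.2–4.4% and 4.8–5.0% without deletion.
- Bonferroni over six follow-up visits (an assumed family, from the seven visits in the payment schedule under Recruitment Procedures), n = 20: family-wise error 6.1–8.9%, against 4.2–4.4% without deletion. At r = 0.9 it is 4.9%.

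Neither provision reliably removes the inflation, and neither acts on the bias.

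**The case against.** The strongest case against is about size, not about whether the rule exists.

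- **High correlation or a large effect leaves little harm.** This stands. The documents give no correlation. The Background reports a 68.29% fall in the Beck Anxiety Inventory in five participants of a different trial; this cannot be converted to SD units, but a large effect is a fair case to show.
- **Some readings keep 5%.** True, but limits pooled over both visits do so by understating the change, and the plan does not say which reading applies.
- **The named test is a within-person comparison.** Participants are selected for high anxiety scores, so scores may change without any drug effect. A rise from 5% to 6–8% in this test is therefore not the false-positive rate of the randomised comparison, for which no test is written. The dose review under Data and Safety Monitoring also turns on a 15% reduction, not a p-value. Both points stand and limit what can be claimed.
- **A fallback and a correction exist.** They are conditional, and nothing says that either replaces the deletion.

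A reader might infer that type I error reaches 10% or that an effect shrinks by 20%. The first needs the rule to act on change scores, which the text supports less well. The second needs change scores with limits pooled over arms in a two-sample test that the plan does not name. A reader might also infer a strict choice between inflation and shrinkage; limits pooled over arms with a within-arm test show that both can occur.

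**Conclusion.** The concern holds. As written, the rule discards valid observations, and its undefined terms leave open which distortion follows. On the literal reading with the named test, that is a type I error of about 6.0–8.2%, or a true change of 0.5–1.0 SD understated by about 5–15% with power at 0.5 SD and n = 20 lowered by about 7 to 8 percentage points (44 to 36; 78 to 71).

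These sizes rest on an assumed 5% level, normal data, correlation 0.3–0.7 and one pass. The distortion is moderate, and it is small at correlation 0.9. It still deserves correction before analysis, because the rule acts on the data behind every outcome and can move a result in either direction. Keeping all valid values restores about 5% type I error and an unbiased estimate under the same assumptions.

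**What to change.** Delete the automatic exclusion and put in its place:

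> All valid observed values are kept in every main outcome analysis. A value is corrected or set to missing only if it is documented to be a recording error or technically invalid (for example, failed imaging quality control by a criterion set in advance). This is decided before unblinding (double-blind phase) or before outcome analysis begins (open-label phase). Any analysis excluding values beyond 2 SD is a labelled sensitivity analysis that states the scale, the group and the number of passes.

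The wording speaks of every main outcome analysis because the plan designates no primary analysis for this trial.

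The cost is a change of text, with no new data or visits. The downside is slightly wider confidence intervals, and genuine extreme values stay in the mean. The plan's existing non-parametric fallback partly covers that case.
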